## 1.0 Objectives

Increased duration of untreated psychosis (DUP), defined as the time from manifestation of the first psychotic symptom(s) to initiation of evidence-based treatment, is associated with poorer clinical and functional outcomes (Fusar-Poli et al., 2009). Factors associated with longer DUP include perceived barriers to care among those experiencing psychotic-like symptoms and feelings of not being listened to or not being offered the opportunity to make decisions regarding treatment (referred to as shared-decision making). The primary objective of our proposed study is to investigate the association between DUP and perceptions regarding barriers to care and shared-decision making among college students. The secondary objective is to conduct a process evaluation of the inclusion of a screening tool (the Prodromal Questionnaire Brief- PQ-B developed by Loewy et al., 2011) during triage at University of New Mexico Student Health and Counseling Center (SHAC). SHAC implemented the PQ-B August 1st, 2020 to improve quality of clinical services by identifying students at risk of first episode psychosis (FEP) and referring those identified at high risk to coordinated specialty care programs (i.e., Early and CONNECT) in the Department of Psychiatry and Behavioral Sciences, University of New Mexico. The Early Program is a coordinated specialty care program for the young adults experiencing first episode psychosis (FEP) while the CONNECT program provides stepped care to young individuals at clinical high risk (CHR) of developing psychosis.

The specific aims are to:

1. Measure DUP among University of New Mexico (UNM) college students enrolled in the Early or CONNECT Programs in the Department of Psychiatry and Behavioral Sciences and identify other factors that may contribute to longer DUP, such as perceptions relating to barriers to mental health care and shared decision-making. We hypothesize that there will be: (1) a positive association between DUP and the number of perceived barriers to care, and (2) a negative association between DUP and feelings of shared-decision making.
2. Collect process level data related to the implementation of the PQ-B at SHAC, including the number of PQ-Bs completed by students at SHAC; the number of students who meet the cut-off score on the PQ-B; responses to specific items on the PQ-B; and basic demographic and clinical characteristics for those who complete the PQ-B [i.e., age, gender, ethnicity, level of education, feelings of depression as measured by the Patient Health Questionnaire-9 (PHQ-9) and feelings around alcohol use as measured by the CAGE. CAGE stands for Cut, Annoyed, Guilty and Eye based on the four questions in the screening tool that indicates a substance abuse problem. The four questions include: (1) Have you ever felt you should cut down on your drinking? (2) Have people annoyed you by criticizing your drinking? (3) Have you felt bad or guilty about your drinking? And (4) have you ever had a drink first think in the morning to steady your nerves or to get rid of a hangover (eye-opener)? All of these data are collected as part of standard clinical practice at triage among students seeking services at SHAC. Among those students who meet the cutoff, we are also interested in tracking the number of students who are referred to Early and CONNECT and, if not referred, the reasons for not being referred.

## 2.0 Background

2.1 General Background. Clinical and general population studies on FEP have generated enough evidence to have confidence in three issues. First, the DUP is a strong predictor of outcome, such that current clinical recommendations are <3-6 months

PROTOCOL TITLE: Duration of Untreated Psychosis and Perceived Barriers to Mental Health Care Among College Students

(Compton et al., 2008). Second, in the U.S., individuals are still presenting with DUP on average of two years (Marshall et al., 2005). Third, the reasons for treatment delay are multiple and complex (Apelodoorn et al., 2014). Various classifications have been developed to categorize the factors that contribute to an extended DUP. Compton and Broussard (2011) for example, identified six categories, including: (i) demographic, (ii) premorbid and onset-related, (iii) illness-related, (iv) family-level, (v) societal, and (vi) health system and service level factors.

With the first symptoms of psychosis being most likely to surface around ages 15 to 24, college age young adults are at increased risk of FEP and CHR of psychosis (Kessler et al., 2007; Simon et al., 2017). Studies on the course of schizophrenia indicate that the initial onset of the disorder shows a steep increase during adolescence and young adulthood and then begins to decrease around the age of 25 (Hafner et al., 1993; Sham et al., 1994). Simon et al., (2017) reported a FEP incidence rate of 86 per 100,000 among ages 15-29 compared to 46 per 100,000 among 30-59 across a variety of care settings. There are other environmental risk factors unique to college students that may increase risk of psychosis and contribute to increased DUP. First, attending college can be a stressful time for many students, learning to live independently and handle college level work load. Second, there are higher rates of illicit and prescription drug use among college students. Third, lack of identification of mental health symptoms and/or treatment have surfaced as system-level challenges on college campuses. This contributes to the persistence of mental health problems among students, partly due to the under-resourcing of college mental health services in relationship to needs. Lastly, many college students are in the process of transitioning between adolescence to adulthood and may be less likely to recognize when to seek help or to feel comfortable with accessing services independent of family support.

Screening has been shown to be a valid and reliable way of identifying individuals at high risk of psychosis, and those who have a higher likelihood of transition to psychosis in various contexts for clinical referral (Jarrett et al., 2012; Kline and Schiffman, 2014). When Rietdijk and colleagues screened all individuals between the ages of 18 and 35 entering secondary mental health services for non-psychotic conditions with the Prodromal Questionnaire (PQ) 92-item version, a three-fold higher prevalence of at-risk mental states was detected among the population that was universally screened compared to a population that was referred to a diagnostic center of an early psychosis clinic based on clinical concerns alone (Rietdijk et al., 2012). Studies on the effectiveness of screening for psychosis among college students are scarce. Loewy et al., assessed the rates of self-reported “prodromal” psychotic symptoms and related distress among 1,020 college students at a university in California using the PQ 92-item version (Lowey et al., 2007). Forty-three percent of students reported  $\geq 8$  items (the suggested cutoff from the initial PQ validation study). The proportion was 2% when the cutoff was modified to  $\geq 8$  items rated as distressing (the addition of a *distress* qualifier is intended to improve specificity and thereby reduces the number of false positives). A Chinese version of the PQ-16 was used to determine the prevalence of attenuated psychotic syndrome among 579 college students in China (Chen et al., 2014). Using a cutoff of  $\geq 6$ , 9.3% screened positive. Among 49 who completed a follow-up interview, 20 (40%) met the criteria for a prodromal risk syndrome as per the Structured Interview for Psychosis-Risk Syndrome (SIPS) diagnostic criteria.

**PROTOCOL TITLE: Duration of Untreated Psychosis and Perceived Barriers to Mental Health Care Among College Students**

**2.2 Scientific Rational.**

Little is known about DUP among college students. Our research will fill this gap. With respect to barriers to care, research has shown that as high as 85% of college-age students do not seek treatment when experiencing a mental health problem (Blanco et al., 2008) despite estimates of mental health problems among college students ranging from 9% to 33% (Hunt and Eisenberg, 2010). Not engaging in treatment for mental health problems can significantly interfere with educational outcome (Eisenberg et al., 2009). There are numerous barriers that hinder access to mental health services, especially for college age young adults. Barriers include, for example, stigma, negative attitudes about treatment providers, poverty, lack of symptom recognition, lack of knowing where to get help, lack of transportation, and feelings of disempowerment (Jennings et al., 2017). Furthermore, in the literature on why people fail to engage or disengage from care, not feeling listened to and not being offered the opportunity to make decisions and collaborate in treatment (O'Brien et al., 2009) have been identified as contributors. Indeed, shared-decision making, an approach to providing person-centered care, has been shown to be a critical factor associated with engagement in coordinated specialty care for first episode psychosis (Hamilton et al., 2018; Heinssen et al., 2014). The goal will be to transfer what we learn about perceived barriers to care and shared-decision making into practice by developing strategies or interventions to reduce the modifiable barriers or increase feelings of shared-decision making so that fewer college students will go without necessary mental health care and specialty services.

While research on screening for first episode psychosis among college students is limited, in general behavioral health-related screening (e.g., for depression, suicidal ideation, alcohol use) among college populations has proven to be effective and to increase access to care (Shepardson et al., 2014). As summarized by Savill et al., "Screening for psychosis may represent a fast, effective solution to identification of early psychosis, without the need for additional expertise" (pg. 689) Savill et al., 2018).

**2.3. Contribution to the Literature.** Upon successful completion of the proposed research, we expect our contribution to the literature to be preliminary data on DUP among college students and perceptions regarding barriers to receiving mental health care and shared-decision making.

The quality improvement data will also contribute to the literature on screening for first episode psychosis among a college population.

**3.0 Inclusion and Exclusion Criteria**

**3.1 Screening for Eligibility.** Screening will be conducted among UNM college students who present to either Early Program or the CONNECT Program, Department of Psychiatry and Behavioral Sciences for an intake assessment. The Early Program is a coordinated specialty care program for the young adults experiencing a FEP while the CONNECT program provides stepped care to young individuals at clinical high risk of developing psychosis. Evidence of psychosis or psychosis risk syndrome will be assessed during the intake visit through a clinical assessment and the Structured Interview of Prodromal Symptoms (SIPS) (Miller et al., 2003) The SIPS will be completed by Early or CONNECT Program clinicians, who are certified in its administration. The SIPS is a structured diagnostic interview and includes the Scale of

**PROTOCOL TITLE:** Duration of Untreated Psychosis and Perceived Barriers to Mental Health Care Among College Students

Prodromal Symptoms (SOPS); Schizotypal Personality Disorder Checklist, a family history questionnaire and a well-anchored version of the Global Assessment of Functioning Scale. The SIPS takes approximately 60-90 minutes to complete depending on clinical status. Those determined eligible for either program based on the clinical assessment and SIPS will be invited to participate in the study. A copy of the SIPS has *not* been included as attachments as it is a copyrighted instruments. More information about the SIPS can be found on the Prime Psychosis Prodrome Research Clinic website.

[https://medicine.yale.edu/psychiatry/research/programs/clinical\\_people/prodome.aspx?organizationId=109519](https://medicine.yale.edu/psychiatry/research/programs/clinical_people/prodome.aspx?organizationId=109519).

It is important to note that patients who enter either program may complete other clinical assessments as part of standard clinical care. While results from these assessments will not be used to determine eligibility for this study, they *may* be used in the proposed study to describe the study population. We will be asking permission to use the data from these standard clinical assessments through the consent process.

***3.2 Inclusion and Exclusion Criteria.*** Eligible participants included in the study will be: (1) 15-30 year-old UNM college students who present to the UNM Early Program or the UNM CONNECT program for an intake, (2) who screen positive for clinical high risk or FEP, and (3) agree to participate in the study. Participants will be excluded if: (1) they are below the age of 15 years old or above the age of 30, (2) are not UNM college students, (3) screen negative for clinical high risk or FEP, (4) refuse to participate in the study, and/or (5) are cognitively unable to provide informed consent as demonstrated by a brief cognitive screen prior to completion of the enrollment interview. Cognitive capacity to consent to research participation will be assessed by the research coordinator using the form included in Attachment 1 - *Evaluation to Sign an Informed Consent Document for Research*.

There are no exclusion or inclusion criteria specific to the PQ-B screening tool implemented at SHAC. The triage process at SHAC has included universal screens for depression, anxiety and substance use for years. As of August 1st, 2020, SHAC extended the universal screening to include risk of psychosis through the inclusion of the PQ-B. Universal screening means that all students who seek counseling services at SHAC complete the PQ-B at triage.

**Inclusion of Special Populations.**

***Adults unable to consent:*** Those determined unable to provide consent through the brief cognitive screen in Attachment 1 will not be enrolled in the study (see Attachment 1 - *Evaluation to Sign an Informed Consent Document for Research*).

***Individuals who are not yet adults (infants, children, teenagers):*** While we expect the majority of participants to be between 18 and 30, participants as young as 15 may be enrolled into the study. Participants younger than 18 will indicate their assent to participate in the study by signing a child assent form, which will be co-signed by a parent or legal guardian (See consent form). Both the child and the parent/ legal guardian must consent for the participants between the ages of 15 and 17 to participate in the research.

**PROTOCOL TITLE:** Duration of Untreated Psychosis and Perceived Barriers to Mental Health Care Among College Students

According to UNM main campus enrollment reports, approximately 1% of students are less than 18 years of age. While it will be unlikely that a student less than 18 years of age will complete the PQ-B the NM Statutes stipulate that *"A child fourteen years of age or older has the right to consent to and receive individual psychotherapy, group psychotherapy, guidance counseling or other forms of verbal therapy and information regarding such counseling is confidential. This means that students ages 16 or 17 who enter SHAC for counselling will be asked to complete the PQ-B as part of standardized SHAC triage process"*

**Pregnant women:**

Pregnant women are not the focus of this study, and research deals with mental health issues of the young in general.

Students at SHAC may be pregnant when accessing counseling services. As a result, they may complete the PQ-B screening tool. There is no evidence to suggest that the completion of the screening tool will be harmful to pregnant women.

**Prisoners:** Prisoners will not be included in the study.

Prisoners will not be completing the PQ-B screening tool. Only students seeking counseling services at SHAC will complete the screening tool.

## **4.0 Study-Wide Number of Subjects**

Not Applicable - This is not a multicenter study – see Section 22 for number of subjects

## **5.0 Study-Wide Recruitment Methods**

Not Applicable - This is not a multicenter study – see Section 21 for number of subjects

## **6.0 Multi-Site Research**

Not Applicable - This is not a multicenter study

## **7.0 Study Timelines**

*7.1. Duration of an individual subject's participation in the study.* Participation in the study is brief. Data will only be collected at one time-point, which will be after the consent process.

*7.2. Duration of anticipated time to enroll all study subjects.* It is expected that all participants will be enrolled by one year from the start of the study.

*7.3. Estimated date for the investigators to complete this study (complete primary analyses)*

It is expected that data analyses will be ongoing throughout the study and that final analysis and publication of study data will occur in the 12-months following the end of study enrollment.

## **8.0 Study Endpoints**

*8.1 Primary and secondary study endpoints.* This is not an outcome study, data will only be collected at one time-point, which will be immediately following the consent process.

*8.2 Primary or secondary safety endpoints.* NA

## 9.0 Procedures Involved

9.1 *Overview of the study design.* The study will use a correlational research design in which we will collect data for each participant only once.

*Overview of research procedures being performed and when they are performed.* Participants will be recruited among UNM college students and who are determined eligible for the proposed study (see inclusion criteria Section 3.2). Once determined eligible, individuals will be invited to participate in the research. Those who agree to participate will complete the consent process. The research coordinator ([name]) or PI ([name]) will be responsible for consenting the individual and data collection. Data will be collected through completion of standardized tools that have all been determined to be reliable, valid and appropriate for the study population (described in 9.3). Data will be collected either through (i) face to face interviews, (ii) phone, or (iii) HIPAA Compliant Zoom Account. These last two options have been put in place to accommodate the social distancing and public health stay at home orders that have been put in place by the NM Governor during COVID. Data will be collected after the consent process. We will aim to collect data at one point in time. However, due to the illness associated with the target population, we may need to split the interview over two time periods. Participants will be provided with a \$20.00 amazon merchandise card per hour to standardized compensation across participants. We will always round up. For example: if a participant completes the surveys in 45 minutes we will give them a \$20.00 merchandise card; if a participant completes the surveys in an hour and a half we will give them two \$20.00 merchandise cards.

9.2 *What data will be collected, including long-term follow-up.* This is not an outcome study so no long-term follow-up data will be collected. Data will only be collected at one-point, following the consent process. In addition to the SIPS, which will be completed by clinicians during the determination of eligibility process, participants will complete the instruments listed below. Noteworthy, is that during the consent process, we will ask students their permission to use their data collected during the determination of eligibility process as well as data from other standard clinical assessments that were conducted on intake. The following instruments will take approximately 2-3 hours to complete.

**Demographic Data:** Basic demographic data will be collected on each participant, including city of birth, phone number and email (for future contact), current education year, date of birth, sex, gender, race and ethnicity. City of birth and full date of birth are required to obtain a Global Unique Identifier (GUID) in the NIMH Data Archive. A GUID is a subject ID allowing researchers to share data specific to a study participant without exposing personally identifiable information. A copy of the demographic form has been attached.

**Structured Clinical Interview for DSM-5 (SCID-5)** (First et al., 2015). The SCID-5 Research Version will be used to confirm clinical diagnoses for all participants enrolled in the research study. Only the sub-units for psychosis, mood disorders, substance abuse and trauma-related disorders will be completed. The SCID-5 will be administered by the research coordinator who has been trained in its use and achieved sufficient reliability for research purposes.

**Duration of Untreated Psychosis (DUP)** will be collected using the Circumstances of Onset and Relapse Schedule (CORS) (Norman and Malla, 2002). The CORS includes

**PROTOCOL TITLE:** Duration of Untreated Psychosis and Perceived Barriers to Mental Health Care Among College Students

the Topography of Psychotic Episode (TOPE), which together traces the process of seeking treatment by identifying step-by-step contacts with medical and mental health services in the pathway toward contact with early psychosis services. The CORS protocol includes specific questions and follow-up prompts to help determine the onset of prodromal and psychotic symptoms and pathways to care (Attachment 2). The CORS has well established psychometric properties and takes approximately an hour to complete. It will be completed by the Research Coordinator or PI through semi-structured interviews. While participants identified as at CHR for psychosis, by definition, would not yet have had a psychotic episode, we will similarly record onset of attenuated psychosis symptoms in order to better understand barriers and pathways to care for this group.

Barriers to care data will be collected using the Barriers to Seeking Psychological Help Scale (BSPHS) that was developed to measure barriers related to psychological help-seeking for college students (Topkaya et al., 2017). The BSPHS is a self-report survey with established psychometric properties. It includes 17 items measured on a 5-point Likert-type scale ranging from strongly disagree to strongly agree (Attachment #3). The items are summed, and higher scores indicate higher obstacles. We added an open-ended question to the BSPHS that provides an opportunity for participants to identify barriers not addressed, such as cultural beliefs that impede help-seeking. We determined this additional item to be important given the high prevalence of Hispanics, and to a lesser extent, Native Americans among our target population. The BSPHS takes approximately 5 minutes to complete.

Data on shared-decision making will be collected via the CollaboRATE Shared Decision Making in Clinical Encounters PhenX Measure (Barr et al., 2014; Forcino et al., 2018). CollaboRATE is a component of the PhenX Toolkit, a set of well-established and validated measures relevant to biomedical research chosen by consensus of domain experts and sponsored by National Institute of Health. CollaboRATE is self-administered and includes 3-items scored on a 5-point Likert-type scale. Higher scores indicate greater shared decision making. It takes about a minute to complete. A copy of CollaboRATE is attached (#4).

The PQ-B is completed during triage by all students seeking counseling services at SHAC. The PQ-B takes approximately 2-3 minutes to complete and is completed electronically. The PQ-B is a self-report checklist of symptoms associated with psychosis and psychosis risk syndromes. Respondents indicate whether they have had any of the 21 thoughts, feelings and/or experiences in the past month by checking "yes" or "no". They are asked to exclude any experiences that occurred only while under the influence of alcohol, drugs, or medications that were not prescribed to them. If respondents answer yes to any of the items, they are then asked to indicate how distressing that experience had been on a Likert-type scale ranging from "strongly disagree" to "strongly agree". Two scores are generated, a total PQ-B score and a total distress score. A copy of the PQ-B is attached.

A counselor at SHAC ([name]) will maintain and share a limited dataset with the research team which will include process level data related to the implementation of the PQ-B at SHAC. The limited data set includes two dates: the completion date of the PQ-B and, for those students who meet the cutoff on the PQ-B, the date of referral to Early and/or CONNECT. These dates are required in the process evaluation to be able to describe the number of PQ-Bs completed and referrals on a monthly basis. A list of the variables that will be included in the limited dataset is attached. The variables

**PROTOCOL TITLE:** Duration of Untreated Psychosis and Perceived Barriers to Mental Health Care Among College Students

selected will allow us to summarize, at an aggregate level, the number of PQ-Bs completed by students at SHAC; the number of students who meet the cut-off score on the PQ-B; responses to specific items on the PQ-B; and basic demographic and clinical characteristics for those who complete the PQ-B (i.e., age, gender, ethnicity, level of education, presence of co-occurring symptoms of depression as measured by the PHQ-9, and signs for alcohol dependence as measured by the CAGE). Among those who meet the cut-off, the limited dataset will include information on who was referred to Early or CONNECT and among those not referred, the reasons for not being referred.

[name] will be responsible for assigning a unique identifier to every student at SHAC and this unique identifier will be entered into the excel spreadsheet that will be shared with the research team. The limited data set will be shared and stored on a shared drive created by HSC IT. The shared drive is located under the secure Psychiatry O: drive. Only [name], [name], [name] (SHAC, Counseling Director) and [name] have access to this shared drive. The limited data set excel sheet is also password protected.

A letter from [name], SHAC Counseling Director supporting this sharing of information has also been attached.

A chart review will also be conducted for those students who were referred to CONNECT and completed a SIPS, but were then determined ineligible for enrollment in the program based on the results. These students were never enrolled in Early or CONNECT and were therefore never eligible to be enrolled in the R34 research project. We will access their EHR to get basic demographics such as sex, gender, race and ethnicity, age at assessment as well as the results of their SIPS assessment to determine why students were deemed ineligible. These limited deidentified data will be entered into a password protected excel spreadsheet.

One of the goals of this study is to determine if the Prodromal Questionnaire-Brief (PQ-B) is an appropriate psychosis screening tool among a college population. We currently have three excel files that have been populated over the study period.

The first excel file (referred to as the triage limited database) is maintained by SHAC. This excel file includes demographic (e.g., gender, age, ethnicity, program year) and clinical information (e.g., the results of the PQ-B, PHQ-9 and CAGE) of all students who complete the PQ-B. To de-identify these data, SHAC assigns unique identifiers to students.

The second excel file (referred to as the secondary phone screen database) is maintained by the Department of Psychiatry and Behavioral Sciences. This excel file includes information on students who are referred to coordinated specialty care (CONNECT/Early) and who contacted the 888-referral number. 237 people in total called the 888-referral number. Of those 237 students, only 57% (n = 136) signed a Release of Information (ROI) which allowed us to look up their demographic and clinical data in the database maintained by SHAC. Because we do not have an ROI for 43% (N = 101), we are missing PQ-B scores, and other valuable demographic and clinical information. As a result, we are unable to fully understand the PQ-B scores among those students who are referred to coordinated specialty care, who ends up completing a secondary screen and who eventually gets enrolled. With missing information on demographic and clinical information (including the PQ-B) score on almost half of those students who reached out

**PROTOCOL TITLE:** Duration of Untreated Psychosis and Perceived Barriers to Mental Health Care Among College Students

for a secondary screen we will not be able to determine whether the Prodromal Questionnaire-Brief (PQ-B) is an appropriate psychosis screening tool among a college population (a primary goal of this research).

The third excel file includes 21 participants who were enrolled in the research arm of this study through the PQ-B screening. Nine of these 21 participants did not sign an ROI at SHAC to allow access to their PQ-B scores. This is a critical piece of data we need in order to get a full picture of how this screening tool identifies individuals at risk for psychosis.

To address this limitation, we are proposing to use an honest broker process to merge all three databases to allow us to fully understand what PQ-B scores indicate clinically within this population. An honest broker is an IRB recommended practice for merging data. We have identified [name] (statistician and Department of Psychiatry and Behavioral Sciences faculty member) to serve as the honest broker.

Using the master key with client names and unique identifiers for records in the triage limited database, the honest broker will be responsible for merging the three excel files to create a complete dataset. Once completed, the final merged limited dataset-containing both initial screening information from SHAC, secondary screening information from Psychiatry and research data- will be stripped of any identifying information and returned to the study team.

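### The three-file merge completes the PQ-B scores but, as described, brings in no SIPS result for students found ineligible, so it cannot show whether the PQ-B is an appropriate screen

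*Combined protocol and SAP*

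**What the plan says.** Section 1.0 gives the DUP associations as the primary objective and a process evaluation of the PQ-B at SHAC as the secondary one. Section 9.2 goes further. It lists as a goal to "determine if the Prodromal Questionnaire-Brief (PQ-B) is an appropriate psychosis screening tool among a college population". It then says that, with so much information missing, the team could not tell whether the PQ-B "is an appropriate psychosis screening tool among a college population (a primary goal of this research").

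The missing information is described in the same section. For the phone-screen file, "237 people in total called the 888-referral number", and "Because we do not have an ROI for 43% (N = 101), we are missing PQ-B scores". For the research file, "Nine of these 21 participants did not sign an ROI at SHAC to allow access to their PQ-B scores". The remedy is that "the honest broker will be responsible for merging the three excel files to create a complete dataset". The three files are SHAC triage (all PQ-B completers), the secondary phone screen (referred students who called) and the 21 research enrollees.

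Section 9.2 also describes a separate chart review of "students who were referred to CONNECT and completed a SIPS, but were then determined ineligible for enrollment in the program". The sentence continues that ineligibility rested on the SIPS results. These data go into their own spreadsheet, and section 11.3 describes a unique identifier assigned for it.

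Section 11.1 plans aggregate summaries of PQ-B process data. It does not say what would count as appropriate, and it names no analysis of PQ-B score against SIPS result.

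**The concern.** To judge a screening questionnaire, its score has to be set against a reference result, in people who turn out positive and in people who turn out negative. Here the reference is the SIPS with clinical assessment at Early or CONNECT intake (section 3.1). The protocol treats missing PQ-B scores as the whole problem. If the negative side of the reference is also absent from the merged file, complete PQ-B scores will not answer the question asked.

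At stake is what the study can say about the PQ-B. Without SIPS results for ineligible students, the natural comparison is enrolled against non-enrolled callers. If enrolled means enrolled in the research study, the non-enrolled group may mix students found ineligible on the SIPS, students who declined the study and students who never had a SIPS. A difference in PQ-B scores between such groups could be reported as evidence about the screen when it partly reflects who agreed to take part.

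**Working it through.** **1. The protocol's own counts (section 9.2).** 136 + 101 = 237; 136/237 = 57.4% and 101/237 = 42.6%, matching the stated 57% and 43%. Among enrollees, 9/21 = 42.9% lack an ROI, leaving 21 − 9 = 12 with one. The counts are consistent.

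**2. What the merge supplies.** At best, and assuming every caller and enrollee has a triage record, PQ-B scores become known for 237/237 callers and 21/21 enrollees. The obstacle the protocol names is then removed.

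**3. Where a SIPS result is described.**

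| File | Who is in it | In the merge? | SIPS result described? |
|---|---|---|---|
| SHAC triage | all PQ-B completers | yes | no |
| Phone screen | referred students who called | yes | none described; variables not fully listed |
| Research | 21 enrollees | yes | positive by eligibility (section 3.2) |
| Chart review | CONNECT referrals ineligible on SIPS | not listed | yes, but no PQ-B score listed |

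Section 3.2 requires a positive screen for clinical high risk or first-episode psychosis, so every one of the 21 is on the positive side. The only file described as holding ineligible SIPS results is the one outside the merge. The master key in section 9.2 covers triage records, and no link from it to the chart-review sheet is described.

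**4. Consequence for a confirmed proportion.** Among students with both a PQ-B and a described SIPS result, the merged file gives 21/21 by construction, whatever the quality of the PQ-B. With m SIPS-negative students linked, it becomes 21/(21 + m). The protocol does not give m. For assumed values of 5, 20 and 80:

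- 21/26 = 81%
- 21/41 = 51%
- 21/101 = 21%

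These only illustrate how far the answer depends on the omitted sheet. They are not estimates, and they assume that all 21 enrollees link.

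**5. Below the cut-off.** Referral is tracked among students who meet the cut-off (section 1.0, aim 2; section 9.2). Section 3.1 applies the SIPS to any UNM student presenting for intake, so a student below the cut-off could be seen by another route, but only incidentally. Sensitivity needs the number of cases below the cut-off, and specificity needs the number of non-cases on both sides. Neither is collected systematically.

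**The case against.** **The protocol promises no accuracy figures.** It never mentions sensitivity, specificity or predictive value. Section 2.3 speaks of preliminary and quality improvement data, and counts completed, above the cut-off and referred are already planned. This limits the point: the process evaluation itself is sound. But section 9.2 sets a stronger goal than section 1.0 and says the merge will show what the scores mean clinically. That claim needs a reference result.

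**The phone-screen file may hold outcomes.** Its variables are not fully listed, and the protocol wants to learn "who ends up completing a secondary screen and who eventually gets enrolled". If that means program enrolment, which rests on the SIPS, the file may carry a SIPS-based outcome. This stands, so the conclusion is limited to what is described, and the fix asks for the file's contents to be stated.

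**Linkage may be easy.** The master key holds client names. Because names are removed from the public text, one cannot tell whether the identifier schemes share an owner. So linkage is undescribed, not shown to be impossible.

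Four stronger readings are tempting and not supported:

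- *Every caller outside the 21 lacks a SIPS result.* The chart-review students do have one, how many of them called is not stated, and the phone-screen file is not fully described.
- *The ineligible students may have been excluded for reasons other than the SIPS.* Section 9.2 ties ineligibility to the SIPS results; only the specific findings remain to be abstracted.
- *The ROI gap is harmless because enrolment looks similar with and without an ROI.* Enrolment rates say nothing about the missing PQ-B scores.
- *The study's main aim fails.* The DUP aim does not use this merge.

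**Conclusion.** The point holds as a limit on what the merged data can support. As described, the merge fills PQ-B gaps for up to 101 callers and 9 enrollees and adds no ineligible SIPS result. Assessment below the cut-off is not systematic. The data can describe PQ-B scores along the referral pathway; they cannot establish screening accuracy. Sections 1.0 and 9.2 also disagree on whether this work is secondary or primary.

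This rests on two readings: that the three files are the only ones merged, as section 9.2 lists them, and that the phone-screen file holds no SIPS or intake outcome. The second is open. If it proves wrong, the gap above the cut-off narrows, but the one below it remains. The number of ineligible students is not given, so the loss cannot be sized further. This is a cheap improvement to a secondary aim and well worth making while the merge is being arranged.

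**What to change.** 1. Reconcile sections 1.0 and 9.2. Restate the goal as secondary: to describe the referral cascade, and the relation of PQ-B scores to SIPS result among students who have both, whatever their route to intake.
2. State whether the phone-screen file holds an intake or SIPS outcome. Subject to IRB approval, have the honest broker link the chart-review sheet to the triage PQ-B records, where a PQ-B exists, before de-identification.
3. In section 11.1, add PQ-B total and distress scores by actual SIPS finding, and cascade proportions (completed, met cut-off, referred, called, SIPS done) with exact binomial confidence intervals. Report the confirmed proportion only among students with a linked SIPS. Note that study decliners may be missing, because use of the SIPS rests on consent (sections 9.2 and 23.0), and that ineligible Early referrals may be missing, because the chart review covers CONNECT only.
4. State that sensitivity and specificity are not estimable from these data.

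**Cost.** One extra linkage step in a merge already proposed, an IRB modification, and a more modest claim about the PQ-B. The modification must give a basis for linkage: section 9.2 calls the chart-review data de-identified, section 11.3 describes no key to SHAC identifiers, and section 26.0 says consent is not waived. If the IRB declines, items 1 and 4 and the cascade still stand, and the SIPS findings of ineligible students can be reported without PQ-B scores.
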